Corneal "pinch" test added at 40 seconds and 60 seconds irrespective of response at earlier timepoints	Table 1, Section 6.4.3, Appendix 2, and Appendix 3	Consistency with how protocol AG-920-CS301 was conducted
Miscellaneous. administrative clarifications	Section 6.4.3 (phone call days), Appendix 2, and Appendix 4	Improve clarity of protocol and avoid confusion
Changed reference to Investigators Brochure FROM 2020 TO 2021	Sections 1.1 and 14.2	Updated Investigator's Brochure with new clinical data.
Added underlined text: All subjects who discontinue IMP due to a report of an AE must be followed-up and provided appropriate medical care until their signs and symptoms have remitted, stabilized, determined to be chronic, or until abnormal laboratory findings have returned to acceptable or pre-study limits if performed as part of the AE assessment .	Section 3.6.5	Improve clarity of protocol and avoid confusion
Changed name of Medical Monitor	Title page and Section 8.3.3	Change in personnel.

Abbreviations and Terms

Abbreviation	Full text
AE	Adverse event
AG-920	Articaine sterile topical ophthalmic solution
BCVA	Best corrected visual acuity
BOCF	Baseline observation carried forward
CFR	Code of Federal Regulations
COVID-19	Coronavirus Disease 2019
CRO	Contract Research Organization
EDC	Electronic Data Capture
ETDRS	Early Treatment of Diabetic Retinopathy Study
FDA	Food and Drug Administration
GCP	Good Clinical Practices
GLP	Good Laboratory Practices
GMP	Good Manufacturing Practices
HCl	Hydrochloride
ICH	International Conference on Harmonisation
ICF	Informed Consent Form
IEC	Independent Ethics Committee
IMP	Investigational Medical Product
IOP	Intraocular pressure
IRB	Institutional Review Board
ITT	Intent-to-Treat
LOCF	Last Observation Carried Forward
logMAR	Logarithmic Minimum Angle of Resolution
MedDRA	Medical Dictionary for Regulatory Activities
NSAID	Non-steroidal anti-inflammatory drug
OD	Oculus dexter (Right eye)
OTC	Over the Counter
OS	Oculus sinister (Left eye)
PP	Per protocol
PPE	Personal protective equipment
PT	Preferred Term
SAE	Serious adverse event
SAP	Statistical Analysis Plan
SOC	System/Order/Class
SOP	Standard Operating Procedures
TEAE	Treatment emergent adverse event
UPT	Urine Pregnancy Test
US	United States
VA	Visual acuity

Summary

Study Number	AG-920-CS302
Clinical Phase:	Phase 3
Type of study	Efficacy and Safety
Name of Investigational product:	Articaine Sterile Topical Ophthalmic Solution (AG-920)
Duration of treatment per subject	1 day
Objectives and Endpoints:	Primary Objective To evaluate anesthetic efficacy of AG-920 Secondary Objectives To evaluate how long it takes one dose of AG-920 to anesthetize the eye To evaluate how long one dose of AG-920 anesthetizes the eye To evaluate the safety and tolerability of AG-920
	Primary Endpoints The proportion of subjects with no pain at 5 minutes. Secondary Endpoints Mean time to no pain score (onset) Mean duration of anesthetic effect Visual acuity, biomicroscopy, AEs, TEAEs, SAEs, withdrawals due to TEAEs
Subject Population:	Healthy volunteers Exclusion criteria may be found in Section 4.2.
Design:	Randomized, placebo (vehicle) controlled, double-masked, parallel-group.
Visit Schedule:	Study visits will consist of a Screening Visit, a dosing and anesthesia testing visit, and a follow-up visit (by telephone)
Number of Investigational Sites:	1-2 US sites
Estimated Total Sample Size:	120/study; ~60/treatment group
Plan for Data Analysis:	With 60 subjects per treatment group and assuming 15% response in the placebo group, this study will have 88% power to detect a treatment effect of at least 25% ($\alpha=0.05$, two-sided).
Investigational/Comparator Product(s), Dose and Mode of Administration	Subjects will receive a single dose of IMP in one (study) eye. The IMP will be randomized as either AG-920 or Placebo. The study eye will be randomized as either right eye (OD) or left eye (OS). The single dose will be administered by the clinic staff as two drops in the study eye 30 seconds apart.

TABLE OF CONTENTS

CONTACT INFORMATION AND PROTOCOL AUTHORIZATION.....	2
ABBREVIATIONS AND TERMS.....	4
SUMMARY.....	5
1 INTRODUCTION.....	8
1.1 Findings from nonclinical and clinical studies.....	8
1.2 Potential Risks and benefits to human subjects.....	9
1.3 Design justification.....	9
2 OBJECTIVES AND ENDPOINTS	9
3 STUDY DESIGN.....	10
3.1 Description and schedule of visits and procedures.....	10
3.2 Measures taken to minimize/avoid bias.....	12
3.3 Study medications	12
3.3.1 IMP Packaging and labeling.....	12
3.3.2 Storage of study medication	13
3.3.3 Study medication accountability.....	13
3.4 Expected duration of subject participation.....	13
3.5 Randomization and procedure for breaking the code	13
3.6 Participant and Study completion	14
3.6.1 Completed subject	14
3.6.2 Non-completing subject/Subject Withdrawal	14
3.6.3 Discontinuation of the Study	14
3.6.4 Discontinuation of a Clinical Site.....	15

1 INTRODUCTION

American Genomics is evaluating the formulation of articaine, an approved local anesthetic, for topical ocular use to provide local anesthesia for intravitreal injections. The Sponsor intends to develop Articaine Sterile Topical Ophthalmic Solution (AG-920) for topical ocular use to induce local anesthesia for intravitreal injection. The systemic exposure to articaine after topical ocular instillation is not expected to be greater than that with oral (dental) use of the marketed product, Septocaine® ([Package Insert](#)).

Injections of pharmacologic agents into the vitreous cavity for the purpose of treating various disorders of the retina as well as intraocular inflammatory disease have become the mainstream. In almost all cases, these injections are made through the pars plana. An injection into the eye in this location, with the needle oriented properly, will be posterior to the human lens or an intraocular implant, but anterior to the retina, thereby avoiding damage to these important structures. The pars plana is a zone that rings the eye extending from 3.0 mm to 5.5 mm from the edge of the cornea (Figure 1).

Figure 1: Human Ocular Structure (coronal view)

While topical agents such as proparacaine achieve excellent anesthesia on the external surface of the eye, they do not numb the internal aspect of the pars plana, which is extremely sensitive. Currently, physicians fall into one of two methodologies: either injecting lidocaine under the conjunctiva first and then executing a second injection through the pars plana, or by using topical lidocaine gel and then performing the intravitreal injection. Patients often report moderate to severe discomfort with each of these approaches. The purpose of the AG-920 topical drop would be to allow a technician to apply the topical solution to the eye, allow the articaine to penetrate the pars plana sufficiently to permit the intravitreal injection without undue discomfort. Articaine was selected for this procedure based upon its clinical use in dental procedures, which suggest it penetrates soft tissue and bone.

1.1 *Findings from nonclinical and clinical studies*

Detailed information on nonclinical and clinical studies with articaine including AG-920 is provided in the [Investigator's Brochure \(2021\)](#).

1.2 Potential Risks and benefits to human subjects

Minimal risks are expected with AG-920.

Expected risks for subjects may include a temporary mild to moderate stinging or burning sensation upon instillation of the investigational medical product (IMP). Temporary mild hyperemia may also occur following instillation. For any additional information on AG-920 use, please refer to the [Investigator's Brochure](#).

As this study is to be conducted in healthy subjects, there is no anticipated benefit other than the possibility that a subject's participation in the present study may help others in the future to have more options for local anesthesia before ophthalmic procedures.

Adverse events (AEs) not reported in previous clinical trials but present among subjects in this clinical trial will be communicated to Investigators and to ethics committees or Institutional Review Board (IRBs) in accordance with local regulations.

1.3 Design justification

Route of administration, dosage, dosage regimen, and treatment period(s)

For more details, please refer to the [Investigator's Brochure](#).

The selected dose of the investigational medicinal product AG-920 is [REDACTED] Articaine Sterile Topical Ophthalmic Solution which contains 80 mg/mL of Articaine Hydrochloride (HCl).

The intended route of administration for AG-920 is topical ocular in this study. Each dose will consist of two drops 30 seconds apart in the study eye. This study consists of a single treatment and subjects will be randomized 1:1 to AG-920 or Placebo.

2 OBJECTIVES AND ENDPOINTS

Primary Objective

To evaluate anesthetic efficacy of AG-920

Secondary Objectives

To evaluate how long it takes one dose of AG-920 to anesthetize the eye

To evaluate how long one dose of AG-920 anesthetizes the eye

To evaluate the safety and tolerability of AG-920

Primary Endpoints

The proportion of subjects with no pain at 5 minutes.

Secondary Endpoints

Mean time to no pain score (onset)

Mean duration of anesthetic effect

Visual acuity, biomicroscopy, AEs, TEAEs, SAEs, withdrawals due to TEAEs

3 STUDY DESIGN

Randomized, placebo-controlled, double-masked, parallel.

3.1 *Description and schedule of visits and procedures*

This is a Phase 3, randomized, placebo-controlled, double-masked, parallel-group design study in healthy subjects performed in the US. It is designed to evaluate the safety and anesthetic efficacy of one dose of Articaine Sterile Topical Ophthalmic Solution (AG-920). In this study, subjects who provide informed consent and fulfill all the inclusion criteria and none of the exclusion criteria will be randomized in a 1:1 ratio to receive a single dose of AG-920 or identical looking placebo into one (study) eye (2 drops 30 seconds apart). Subjects will undergo a conjunctival pinch procedure and the pain associated with the pinch rated. IMP dosing and conjunctival pinch procedure will be performed by the study staff.

A schedule of assessments, including allowable visit windows, is displayed in Table 1.

Table 1: Schedule of Visits and Procedures

Procedures	Visit 1		Visit 2					Phone Follow-Up	
	Screening Day -2 to 0/1		Screening & Baseline Day 1 ¹						
	Pre-dose	Dose	20 s post 2 nd drop	40 s post 2 nd drop	60 s post 2 nd drop	5 m	15-60 m post last pinch		
			0 sec	30 sec					
Written Informed Consent	X								
Inclusion/Exclusion Criteria	X		X						
Demographics, Systemic and Ocular Medical History	X								
Concomitant Medication Query	X	X	X					X	
OTC Tear Tolerability	X								
BCVA	X						X		
Urine Pregnancy Test (if applicable)	X								
Biomicroscopy and External Eye Exam	X						X		
IOP Measurement	X								
Randomization		X							
IMP Administration ²		X	X						
Conjunctival pinch ³				X	X	X	X		
Assessment of Pinch Pain				X	X	X	X		
Adverse Event Assessment	X	X	X	X	X	X	X	X	

BCVA = Best corrected visual acuity, IOP = Intraocular pressure, OTC = over the counter, IMP = investigational medicinal product.

See Section 6.4.3 for Windows in Day 1 timing.

3.2 Measures taken to minimize/avoid bias

The Investigator(s), Sponsor, and the subject will be masked to treatment assignment throughout the conduct of the study. Exceptions to this are limited to one statistician at the Contract Research Organization (CRO) who will prepare the randomization code, and three people at the Sponsor who will review the batch records and release product. None of these masked persons will be involved in the day to day execution of the study. The masking will be broken after database lock.

3.3 Study medications

Articaine Sterile Topical Ophthalmic Solution (AG-920) is a sterile, isotonic, non-preserved aqueous solution containing the active ingredient Articaine HCl [REDACTED]

Placebo ophthalmic solution is identical to the active product, with the exception of the active ingredient.

Figure 2: Investigational Medicinal Product

INVESTIGATIONAL PRODUCT		
PRODUCT NAME	Articaine Sterile Topical Ophthalmic Solution (AG-920)	Placebo
ACTIVE INGREDIENT	Articaine Hydrochloride	--
INACTIVE INGREDIENTS	Boric Acid Mannitol Sodium Acetate Trihydrate Glacial Acetic Acid Eddetate Disodium Dihydrate Water for Injection	Boric Acid Mannitol Sodium Acetate Trihydrate Glacial Acetic Acid Eddetate Disodium Dihydrate Water for Injection
UNIT DOSE	0.5 mL blow fill seal vial	0.5 mL blow fill seal vial
ROUTE OF ADMINISTRATION	Topical ocular	Topical ocular
DOSING REGIMEN	2 drops 30 seconds apart from a single vial into study eye	2 drops 30 seconds apart from a single vial into study eye
STORAGE REQUIREMENTS	Store at Room Temperature (15-25°C or 59-77°F)	Store at Room Temperature (15-25°C or 59-77°F)

3.3.1 IMP Packaging and labeling

Investigational Medical Product (IMP) will be packaged and labeled identically in order to maintain the integrity of the double mask. The appearance of the blow fill seal vials for the AG-920 and matching placebo dosage forms are indistinguishable.

The container-closure system to be used for the AG-920 and Placebo in this clinical study is a 0.5 mL low-density polyethylene (LDPE) resin blow fill seal vial. There are 5 vials inside an aluminum foil pouch. Each foil pouch will be labeled with an investigational label with the following minimal information: the study number, kit number, and storage statement, including a statement “Caution – New Drug – Limited by Federal (US) Law to Investigational Use” or equivalent. Each foil pouch will be individually placed into a single-unit carton and a similar investigational label will be applied to the carton. The IMP for each individual treatment assignment will be packaged into identical subject kits.

3.3.2 Storage of study medication

The IMP should be stored at room temperature (15-25°C or 59-77°F). Do not freeze the product. Prior to dispensing to the subject, all investigational material must be stored in a secure location with strictly limited access documented by signature of authorized persons who may dispense investigational materials.

3.3.3 Study medication accountability

Accountability of IMP kits will be conducted by a member of the site and verified by a study monitor. Accountability will be ascertained by performing reconciliation between the number of kits sent to the site and the amount used and unused at the time of reconciliation. Site staff will be queried about any discrepancies.

IMP kit shipment records will be verified, and accountability performed by comparing the shipment inventory sheet to the actual quantity of kits received at the site. In addition, receipt of kits will be confirmed by the study monitor. Accurate records of receipt and disposition of the kits (e.g., dates, quantity, subject number, kits used, kits unused, etc.) must be maintained by the Investigator or his/her designee.

At the end of the study and after the monitor has verified kit accountability, all IMP is to be returned to American Genomics (or designee) or destroyed at the site and documented per the site's standard process.

3.4 Expected duration of subject participation

Each subject is planned to participate in the study for up to 2 Visits (Screening and Treatment/Anesthesia testing) and a Follow-up Phone Call 1-4 days following Visit 2 (Day 2-5).

3.5 Randomization and procedure for breaking the code

A randomization code for allocating the treatments will be prepared by an independent biostatistician, who is not involved in the day-to-day conduct of the study. Subjects will be randomized in a 1:1 ratio to receive AG-920 or Placebo.

Treatment assignments will be masked to the Investigator, the clinical study team (Sponsor, personnel involved in day to day study management, Monitors, Data Managers, and Statisticians), and the subjects. Only in case of medical emergency or occurrence of adverse events that warrant unmasking in the opinion of the investigator, will the treatment assignment(s) be unmasked and made available to the Investigator and the Sponsor Safety Officer. In the absence of medical need, the randomization code will not be available to the above personnel until after the study is completed and the database is locked.

If the Investigator feels it is necessary to unmask a subject's treatment assignment after an emergency situation, the Investigator should contact the Sponsor Safety Officer or designee. Only after consultation with the Sponsor Safety Officer will a decision be made as to whether or not the treatment for the subject should be unmasked. The treatment assignment will be revealed on a subject-by-subject basis, thus leaving the masking on the remaining subjects intact.

If there is an emergency situation in which treatment of an adverse event requires immediate decoding, and the Investigator is unable to contact the Sponsor Safety Officer, the Investigator should treat the subject as if they received active treatment (AG-920) and not placebo. The Investigator should contact the Sponsor immediately and document the AE.

3.6 Participant and Study completion

3.6.1 Completed subject

A completed subject is defined as one who completes all Visits (1 and 2) and the Follow Up Phone call.

3.6.2 Non-completing subject/Subject Withdrawal

A non-completing subject is defined as one who exits the study by their own volition or at the discretion of the Investigator and/or the Sponsor Safety Officer. Any subject may decide to voluntarily withdraw from the study at any time without prejudice and the reason will be documented. In the event that discontinuation of treatment is necessary, the Investigator will make every attempt to complete all subsequent safety assessments. Every attempt should be made to keep subjects in the study and to perform the required study procedures, but if this is not possible, the subject may be withdrawn.

All reasonable efforts should be made to contact the subject who is lost to follow-up. These efforts must be documented in the subject's file.

Subjects may be withdrawn from the study for any reason at any time, including but not limited to the following reasons:

- Subject request
- Use of prohibited concomitant medication/therapy
- Lost to follow-up
- Occurrence of AEs that are not compatible with the continuation of the subject in the study, in the Investigator's opinion, or that make it unacceptable to the subject to continue
- Investigator judgment
- Sponsor request
- Randomization code broken prematurely
- Pregnancy

The reason for early discontinuation will be collected

3.6.3 Discontinuation of the Study

If the clinical study is prematurely terminated or suspended, the Sponsor or designee will inform the Investigators and the regulatory authorities of the termination/suspension and the reason(s) for the termination/suspension. The Investigators should promptly notify their Independent Ethics

Committee (IEC) or Institutional Review Board (IRB) of the termination or suspension and of the reasons.

3.6.4 Discontinuation of a Clinical Site

The Sponsor reserves the right to close an investigational site or terminate the study in its entirety at any time, for reasonable cause. Reasons for the closure of any investigational site or termination of the study may include:

- Failure to accrue subjects into the study at an acceptable rate.
- Failure of the Investigator to comply with applicable regulations and Good Clinical Practice (GCP) guidelines.
- Submission of knowingly false information from the research facility to the Sponsor, Food and Drug Administration (FDA), or other regulatory authorities.
- Insufficient adherence to protocol requirements and procedures.

If the study is prematurely discontinued, all study data must be returned to the Sponsor or designee. Additionally, the site must conduct final disposition of all unused IMP in accordance with CRO procedures. Study termination and follow-up will be performed in compliance with the conditions set forth in regulatory guidelines.

Financial compensation to the Investigator and/or institution will be in accordance with the agreement established between the Investigator and the Sponsor or Sponsor designee.

3.6.5 Actions after discontinuation

All subjects who discontinue IMP due to a report of an AE **must** be followed-up and provided appropriate medical care until their signs and symptoms have remitted, stabilized, determined to be chronic, or until abnormal laboratory findings have returned to acceptable or pre-study limits if performed as part of the AE assessment.

For the subject who chooses to withdraw consent or who is non-compliant, every possible effort should be made by the Investigator to assure there is a final visit that includes all examinations listed for Visit 2.

3.6.6 Completed study

The end of the study is defined as the date the last subject completes the Follow-up Phone Call.

3.6.7 Procedure after the completion of the study

When the study is completed and the site has been closed out, the Investigator will be asked to notify the governing IRB.

4 SUBJECT INCLUSION AND EXCLUSION CRITERIA

Subjects must meet all of the following inclusion criteria to be eligible for participation in this study. On criteria that involves the eyes, both eyes must qualify.

4.1 *Subject inclusion criteria*

1. Provide written informed consent prior to any study-related procedures being performed.

2. Is male or a non-pregnant, non-lactating female aged 18 years or older. Female subjects of childbearing potential must have a negative urine pregnancy test at Screening (Visit 1) in order to be eligible for randomization.
3. Are willing and able to follow instructions and can be present for the required study visits and Follow-up Phone Call for the duration of the study.
4. [REDACTED]
5. Have an Intraocular Pressure (IOP) between 7 and 30 mmHg.
6. Certified as healthy by clinical assessment (detailed medical history) including ocular examination.
7. Verbal communication skills adequate to participate.
8. Able to tolerate bilateral instillation of Over-The-Counter artificial tear product based on investigator judgement.

4.2 Subject exclusion criteria

Subjects who meet any of the following exclusion criteria are ineligible for this study:

1. Have participated in an investigational study (drug or device) within the past 30 days.
2. Have a contraindication to local anesthetics, [REDACTED] or any component of the IMP.
3. Have known decreased corneal or conjunctival sensitivity (e.g., sequelae of herpetic eye disease, corneal graft) or a diagnosed corneal pathology which might lead to decreased sensitivity.
4. Have had ocular surgery (intraocular, refractive, extraocular muscles, eyelid) or general surgery in either eye within the past 90 days (Note: dental restorative work allowed)
5. Have had an intravitreal injection in either eye within 14 days of randomization.
6. Have ocular surface disease requiring punctal plugs.
7. Evidence of any current ocular inflammation.
8. Subject who must wear contact lenses on Study Day 1 (Visit 2).
9. Are currently using, or used within the past 30 days, a systemic opioid or opiate analgesic or topical Non-steroidal Anti-Inflammatory Drug (NSAID).
10. Subject who cannot withhold their intermittent over-the-counter (OTC) artificial tear lubricant products for one hour preceding or following study medication.
11. Any condition, including alcohol or drug dependency, that would limit the subject's ability to comply with the procedures of the protocol (per Investigator's judgment).
12. The subject or a close relative of the subject is the investigator or a sub-investigator, research assistant, pharmacist, study coordinator, or other staff directly involved in the conduct of the study.

Note: Given the approval status and preclinical safety information on the molecule, and low chance of systemic exposure, other than the negative urine pregnancy test, there is no restriction on women of child-bearing potential.

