4.3 Subject replacement

Discontinued subjects may be replaced by enrollment of additional subjects until approximately 120 subjects are enrolled.

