6 STUDY PROCEDURES

6.1 General Procedures:

The study will consist of 1 or 2 clinic visits and 1 Follow-up Phone Call. All ocular assessments will be performed on both eyes. Subjects will be screened for entry (Visit 1) and randomized/treated at (Visit 2). Visit 1 and 2 may be on the same day. At randomization, subjects will receive a single dose of IMP (2 drops 30 seconds apart) in the study eye. Subjects will then have a safety Follow-up Phone Call 1-4 days (Days 2-5) following Visit 2.

6.2 Re-screening Procedures:

A subject who is first designated as a screen failure prior to being randomized will be allowed to rescreen one additional time 7-30 days later.

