6.4.3 Post Treatment and Pinch Test

- [REDACTED] forceps will be used to “pinch” the [REDACTED] conjunctiva of the study eye at the following timepoints. Details on the pinching method will be provided separately:
 - **20 seconds following complete dose administration** (second drop of IMP)
 - **40 seconds following dose administration**
 - **60 seconds following dose administration**
 - **5 minutes following dose administration**
- Immediately following EACH pinch test, subjects will be asked “Was that painful” “Yes” or “NO.” It should be explained to subjects that the feeling of pressure is NOT to be judged as pain. [REDACTED]
[REDACTED].

All subjects are pinched at 20, 40, 60 seconds and 5 minutes post dose. If the subject feels no pain at 5 minutes, the subject will be considered “anesthetized.” Pinching of anesthetized subjects will continue at 10 minutes and EVERY FIVE MINUTES for up to 30 minutes or until pain resumes. Once pain resumes, pinching is stopped.

If the subject experiences pain at 5 minutes, pinching will be concluded and this subject will be considered to NOT have reached anesthesia at 5 minutes.

Within 15-60 minutes after the last pinch test, the following examinations will be performed

- BCVA
- Perform slit lamp biomicroscopy and external eye exam
- Assess for adverse events
- Schedule Follow-up Phone Call between Day 2-5 (1-4 days following dosing).

Windows: Times will be measured to the nearest minute with the exception of the 20, 40 and 60 second time points. Those should be recorded to the second. Times up to 5 minutes post 2nd instillation should be followed. Investigators are allowed a window of \pm 1 minute at the 10 minute time point, and \pm 2 minutes at subsequent time points.

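### The readable eligibility text bars earlier trial participation only within 30 days, so people dosed in AG-920-CS301 before then could enter a trial with a self-reported pain endpoint (minor)

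*Protocol*

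**What the plan says.** Exclusion criterion 1 in Protocol Section 4.2 applies to people who "Have participated in an investigational study (drug or device) within the past 30 days". No readable criterion in Sections 4.1, 4.2 or 5.1 mentions earlier receipt of AG-920, earlier experience of the pinch test, or earlier randomization in another AG-920 study. Inclusion criterion 4 is wholly redacted and exclusion criterion 2 partly so.

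The summary of changes explains the added pinch times at 40 and 60 seconds by "Consistency with how protocol AG-920-CS301 was conducted". An AG-920 trial using a pinch test had therefore been conducted before this amendment. The documents do not give its phase, sites, dates, allocation ratio or population.

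The primary endpoint (Protocol Section 2) is "The proportion of subjects with no pain at 5 minutes". Under Section 6.4.3 the subject answers yes or no after each pinch, with one piece of coaching: "It should be explained to subjects that the feeling of pressure is NOT to be judged as pain". Section 3.2 lists masking of the subject among the measures against bias.

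On re-entry, Section 6.2 says that a subject "designated as a screen failure prior to being randomized will be allowed to rescreen one additional time", and Section 4.3 says "Discontinued subjects may be replaced by enrollment of additional subjects until approximately 120 subjects are enrolled".

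Section 5.1.2 records medications for the 30 days before screening. The subgroups in SAP Sections 2.9.1 and 4.1 are sex, age, race and iris color. The readable SAP text has no analysis by prior AG-920 exposure and no assessment of masking.

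**The concern.** A 30-day limit deals with carry-over of a drug. It does not deal with memory. A subject who has had an AG-920 dose followed by a pinch has a personal reference for how numb the eye became and how the pinch felt. At the next dosing that subject can judge whether the same effect is present, and the judgment may color the yes/no answer that forms the primary endpoint. If recognition moves answers toward no pain on AG-920 and toward pain on placebo, the treatment difference is inflated.

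Return is feasible here: healthy volunteers, 1-2 US sites, one dose, and participation lasting days. Nothing in the readable plan would reliably show it afterwards. The medication record reaches back only 30 days, and although medical history is collected at screening, no item asks about earlier AG-920 studies. What is at stake is confidence in the size of the effect and in the masking, more than the likely direction of the result.

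**Working it through.** **1. The plan's own figure.** Inputs from Protocol Section 9.2 and SAP Section 2.5: 60 per group, 15% response on placebo, a 25-point effect (hence 40% on AG-920), two-sided 0.05, chi-square without continuity correction. With the pooled-variance normal approximation and mean rate 0.275:

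- null standard error = √(2 × 0.275 × 0.725 / 60) = 0.0815
- alternative standard error = √((0.15 × 0.85 + 0.40 × 0.60) / 60) = 0.0783
- power = Φ((0.25 − 1.96 × 0.0815) / 0.0783) = Φ(1.15) = 87.6%

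Exact enumeration gives 88.6%. The stated 88% reproduces. It does not depend on the eligibility gap.

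**2. Who is eligible.** Setting exclusion 1 beside the summary of changes, a person last in AG-920-CS301 on day −31 or earlier meets no readable exclusion on that ground.

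**3. Size of a possible bias, first model.** The documents give no share of returners and no reporting shift, so every input in this step is an assumption.

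- v = share of returners in each arm
- 0.5 = share of them who had active drug before (assumes 1:1 allocation in AG-920-CS301, which is not stated)
- g = share of those who recognize the assignment
- a = upward shift in the no-pain rate on AG-920; b = downward shift on placebo

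Bias in the difference = v × 0.5 × g × (a + b). For example, 0.10 × 0.5 × 0.5 × 0.30 = 0.0075.

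The last two columns give the chance of a significant result favoring AG-920 when both true rates are 15% (exact, uncorrected chi-square, 60 per group; 2.3% with no bias).

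| v | Bias, milder (g = 0.5, a = 0.20, b = 0.10) | Bias, stronger (g = 0.8, a = 0.30, b = 0.15) | False positive, milder | False positive, stronger |
|---|---|---|---|---|
| 10% | 0.75 points | 1.8 points | 3.0% | 4.3% |
| 20% | 1.5 points | 3.6 points | 3.9% | 7.4% |
| 40% | 3.0 points | 7.2 points | 6.2% | 17.9% |

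The stronger set is close to a ceiling: b = 0.15 takes recognizers on placebo from 15% to zero, and v = 40% means 48 of 120 subjects.

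**4. Second model.** Let every returner (share f) shift by +s on AG-920 and −s on placebo, so bias = 2fs. Exact two-sided type I error, with 15% true response in both arms:

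| f | s | Bias | Type I error |
|---|---|---|---|
| 0 | – | 0 | 4.7% |
| 5% | 10 points | 1 point | 5.0% |
| 10% | 10 points | 2 points | 5.7% |
| 20% | 10 points | 4 points | 8.9% |
| 20% | 15 points | 6 points | 14.3% |

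The two models agree: about 1 to 2 points at 10% returners, with clear inflation only from roughly 20%.

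**5. Effect of the remedy on power.** With the exclusion in place and recruitment still to 60 per group, power stays at about 88%. If returners are already enrolled and are left out of a repeat analysis without replacement, the formula in step 1 gives 83.9% at 54 per group (10% removed) and 79.3% at 48 per group (20% removed).

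**The case against.** The strongest objection is that no overlap is shown. The documents name no sites, dates or population for AG-920-CS301, and the redacted criteria might already cover the point. This stands: the gap is in the readable text, and its effect is hypothetical.

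Recognition is also not special to returners. Numbness is the intended effect, so a first-time subject may notice it. Topical anesthetic may be used for the pressure measurement at screening (Section 6.3), and every subject has been pinched three times before the 5-minute assessment. This stands in part. Any subject may guess, but only one with an earlier dose can compare with it; how much that adds is unknown.

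A reader might also infer four stronger points that the documents do not support.

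- **A completer of this trial would be enrolled again.** Section 5 specifies one dose in one eye, Section 3.4 plans up to two visits and a call, Section 6.2 allows rescreening only before randomization, and Section 4.3 speaks of additional subjects. Together these imply no re-entry, although no criterion states a ban.
- **Stinging reveals the active arm.** Section 1.2 attributes stinging or burning to the investigational product, which Section 5 defines as either AG-920 or placebo. The text does not say that the sensation differs between arms.
- **AG-920-CS301 is a confirmatory Phase 3 trial sharing subjects with this one.** Its phase is not stated. The sample-size entry "120/study; ~60/treatment group" hints at more than one study and goes no further.
- **Self-selection of people who tolerate the pinch creates false superiority.** Returners are randomized 1:1, so such selection affects both arms. It bears on the placebo rate and power, not on the validity of the comparison.

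**Conclusion.** The gap is real in the readable text, and minor. Someone treated in AG-920-CS301 more than 30 days earlier is not excluded, the endpoint is that person's own answer about pain, and no planned record or analysis would bring the earlier exposure to light.

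Under the assumptions shown, including that recognition favors AG-920, the bias at 10% returners is below one tenth of the planned effect and the two-sided type I error rises from 4.7% to at most 5.7%. From about 20% returners the inflation can become material. If the true effect is near 25 points, the conclusion is unlikely to change. The documents support neither a claim that masking has failed nor any particular share of returners. The case for acting is that the change is very cheap and that the exposure may be hard to identify later.

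**What to change.** Extend exclusion criterion 1 with the clause: *or have previously been randomized in any study of AG-920 (including AG-920-CS301)*. Have the site check each candidate against its AG-920 enrolment logs at screening. If a redacted criterion already does this, no change is needed.

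If enrolment has begun, flag subjects with earlier AG-920 study participation before unmasking, and add to the SAP a repeat of the primary analysis without them, as a sensitivity analysis.

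The cost is one clause, a log check, and a slightly smaller volunteer pool at any site that also ran AG-920-CS301. For 120 healthy volunteers that is a small burden.
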